Secondary Objectives: To test hypothesis that 12-weeks of BID tvCVS treatments increase functional connectivity in the brain.

Exploratory Objectives: This study will seek to establish the relationships between changes in cerebral perfusion and CVR with improvements in clinical endpoints and to evaluate whether these changes are durable (at an assessment five weeks after the cessation of treatments). Furthermore, the feasibility of detecting change in cerebrovascular reactivity (CVR) as assessed via transcranial Doppler sonography (TCD) will also be explored as well as pulse wave velocity (PWV).

Study Design

A double-blinded, randomized trial comparing two different neurostimulation patterns will explore the effects of tvCVS treatments on changes in biomarkers of neurovascular status (i.e. cerebral blood flow perfusion and cerebrovascular reactivity) as well as their relationship to clinical endpoints. Eligible and enrolled participants will be randomly allocated in a 1:1 ratio using block randomization by the clinical site. Participants will be trained in the clinic to self-administer device treatment and then will continue to self-administer the ~19-minute treatments twice daily for 12 weeks in the home. Individual stimulation sessions will be spaced a minimum of 1 hour apart. Outcome measures will be administered at the baseline, the end of the 12-week treatment period and at 5 weeks post-treatment. Study participants will continue to take their approved PD medications throughout the study and will maintain patterns of usage throughout.

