- Anti-emetics (e.g., 5-HT3 receptor antagonists, D2 receptor antagonists, H1 Receptor antagonists, muscarinic antagonists, synthetic cannabinoids, corticosteroids or SP/NK1 receptors antagonists) prescribed chronically (taken more than 2 times per week, consistently)
- Cannabinoids (e.g., marijuana, tetrahydrocannabinol nabilone or cannabidiol) within 4 weeks of screening.
- Any drug that has not been legalized on a United States Federal level
- Controlled substances that have not been prescribed under the care of a licensed professional.

Sample size:

Up to 20 study participants will be enrolled in the study at one clinical site, Wake Forest School of Medicine, in the United States. Wake Forest School of Medicine (WFSM) has the expertise in the conduct of clinical trials for Parkinson's disease therapeutics. A maximum of 4 participants may be enrolled in any given month.

Interventions and Interactions

Description of Study Intervention

The generation 3.2 TNM™ Device has been approved by the FDA for the prevention of episodic migraine in adolescent and adult patients 12 and older. The Device has been designated as non-significant risk (NSR) by the FDA for studies in PD, and thus, is suitable for home use.

Figure 2. TNM™ device and treatment. (A) Schematic showing device design of the Generation 4.0 TNM device. (B) Patient undergoing treatment while wearing the TNM headset and lying on an incline wedge pillow. (C) Example of target and actual thermal profiles of the saw-tooth, time-varying thermal waveform used for active treatment.

The next generation device (4.0) which has been adapted to improve usability for patients with PD will be utilized in this study. See Scion TNM™ 4.0 Clinical Quick Reference Guide (QRG) for more details. The device delivers software-driven, time-varying thermal waveforms to modulate neural areas, including the brainstem, by means of CVS. The device is fashioned like a set of music earphones, with two independently controlled thermoelectric devices attached to aluminum earpieces that fit inside the ear canals and abut, but do not enter, the bony canals (see Figure 2A). Specific details regarding the device design have been previously published ².

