For the stimulation 2 treatment, no power will be delivered to the heating and cooling elements within the headset. However, the aluminum earpieces, which will be room temperature at the start of the treatment, will provide an initial cooling stimulus when placed within the ear canals, and thus provide a minimal amount of vestibular stimulation. During the treatment, the earpieces will eventually warm to body temperature. Of note, this condition provides the minimum level of stimulation that is possible while keeping the Device the same. All other sensory experiences associated with device treatment will be the same including auditory sensations from the start and stop tones of the device and the faint whirring noise provided by the activity of cooling fans within the headset, the pressure sensations from the headset, the visual displays on the LED screen, and the choreography of staring, conducting and stopping a treatment.

Intended Use:

The TNM™ Device is intended to stimulate the brainstem through the vestibular system via external ear canals using software-controlled thermal waveforms.

Preparation/Handling/Storage/Accountability:

Study devices must be stored in a secure area with limited access. Storage rooms used for this purpose must have locked access. Only delegated research staff should be allowed to enter. Doors shall remain locked at all times.

Upon receipt, the shipment of study devices should be inventoried. Discrepancies or damaged shipments should promptly be brought to the attention of the Device sponsor. Copies of the packing slips should be retained, and the inventory should be documented on the Investigator Inventory Control Form located in the regulatory binder for the study.

Study coordinators should complete the Investigator Inventory Control Form whenever one of the following event occurs: 1) devices are received from the Device Sponsor, 2) devices are dispensed to participants, 3) devices are returned from participants and 4) devices are shipped

back to the Device Sponsor. In the case of a damaged or failed device, coordinators should contact the Device sponsor clinical research associate (CRA) for instructions, as soon as possible.

After the study participant returns the device to the clinic. The study coordinator will then complete a Device Return Document and ship the Device back to Robling using the shipping information provided on that form.

Randomization, Blinding and Unblinding:

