As part of the study intake during Screening Visit, the contact information for both the study participant and the caregiver will be collected and kept confidential and private by the clinical site. During each study visit or interim phone contact, participants will be asked to confirm the date/time of their next scheduled study visit. If a participant misses a scheduled visit or phone call, the coordinator should call the participant the same day to reschedule the visit. The rescheduled visit/call should occur as soon as possible after the missed appointment and within 5 business days. The reason for rescheduling a study visit should be documented. If the participant does not respond within 24 hours, the coordinator will also contact the caregiver. If there is no response from the participant, the coordinator will attempt to contact the caregiver and will continue to contact both the participant and caregiver daily for 1 week or until contact is made. If the prior step is unsuccessful, the coordinator is required to reach out to the participant's caregiver, or other contact(s) provided. If the prior step is unsuccessful, the coordinator is required to reach out to the participant once a week over the next 6 weeks. All contact attempts must be documented. If all telephone attempts are unsuccessful, the coordinator will follow up by sending a letter to the participant.

Study participants will be considered "lost to follow-up" if they are enrolled and participating in the clinical trial, missed a clinical study visit and become unreachable (via phone or mail) during the study.

Analysis Plan

Group-wise comparisons will be made using an analysis of covariance adjusting for baseline severity and white-matter lesion burden. The results by group will be presented as group means/medians and treatment differences with corresponding 95% confidence intervals. Tests for assumptions will be conducted prior to analysis. In the case of non-normality, equivalent non-parametric approaches will be utilized. In order to evaluate whether the physiological changes explored in this study serve as the underlying mechanism for the reduced PD symptoms from TNM™ Device therapy, we will run correlational analyses between the imaging measures and the clinical measures using the change scores from the end of treatment and the post-treatment follow-up relative to the baseline measure.

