Analysis effort will first focus on evaluating changes in cerebral perfusion and cardiovascular reactivity after 12 weeks of tvCVS therapy and how these changes related to those observed in the clinical endpoints. Once these study result have been summarized and provided to the Michael J Fox Foundation, changes in functional connectivity will be explored.

Human Subjects Protection

Risk Benefit Assessment

There is a long-standing history to support the safety of caloric vestibular stimulation (CVS) as a technique as the approach has been used diagnostically for more than a century in patients from infancy through late adulthood. The low incidence of AEs and lack of serious AEs, unexpected AEs or negative sequela on measures of mood, cognition or balance in the previous episodic migraine study ⁴³ supports the safety of the time-varying TNM™ therapy. The low incidence of AEs that could potentially be related to device-use in the PD single-site RCT study ¹ as well as a cross-over study and two case-studies further exemplify the safety of TNM™ therapy in PD populations. The United States Food and Drug Administration has designated the device to be of non-significant risk for studies of Parkinson's disease (and migraine), and thus suitable for home-use.

Prospective participants will be told that the main purpose of the research will be to generate scientific data and to contribute to medical knowledge, regardless of any benefits to individual participants, and that alternative treatments are available. Prospective participants will be made aware of the existence of two different neurostimulation patterns and that they should not necessarily expect that their symptoms will improve as a result of participating in the trial. They will also be told that participants are expected to provide honest and accurate answers and should not worry about disappointing the staff if they do not feel better during the treatment period, rather the most important thing is to accurately report their symptoms. Potential participants should be made aware that for this research partnership, interactions with study personnel are likely to differ from the interaction they typically experience in the therapeutic partnership they experience in the clinic. More specifically, participants should expect that interactions may be

more neutral and focused on data collection than they may be used to on clinical therapeutic visits.

Recruitment Methods

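### The Analysis Plan gives no term for arm in the imaging–clinical correlations; if both arms are correlated together and the device shifts both outcomes, the gap between arm means can create a correlation by itself

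*Combined protocol and SAP*

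**What the plan says.** The Analysis Plan sets the purpose of the correlations as to "evaluate whether the physiological changes explored in this study serve as the underlying mechanism for the reduced PD symptoms". The method is one clause: "we will run correlational analyses between the imaging measures and the clinical measures using the change scores from the end of treatment", with the post-treatment follow-up as a second time point. No coefficient, covariate, significance level or handling of arm is given.

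Arm and covariates appear only for the group comparison: "Group-wise comparisons will be made using an analysis of covariance adjusting for baseline severity and white-matter lesion burden". Its reporting rule is "The results by group will be presented as group means/medians and treatment differences with corresponding 95% confidence intervals".

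The same section returns to the topic when it sets the order of work, looking at perfusion and reactivity changes "after 12 weeks of tvCVS therapy and how these changes related to those observed in the clinical endpoints". That adds no method. Under Objectives the aim is exploratory: "relationships between changes in cerebral perfusion and CVR with improvements in clinical endpoints". Under Sample size, "Up to 20 study participants will be enrolled in the study at one clinical site"; with 1:1 allocation that is about 10 per arm.

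**The concern.** The wording allows two analyses.

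- **Active arm only.** The purpose clause speaks of symptom reduction from device therapy, and the later sentence of change after tvCVS therapy.
- **Both arms together.** Neither sentence restricts the correlations to one arm. Stimulation 2 is also described as a weak stimulus; its earpieces cool the canal at first and "thus provide a minimal amount of vestibular stimulation".

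Under the second analysis, a device that moves perfusion and also moves symptoms yields two clusters of points, one per arm, offset on both axes. A line through the clusters slopes even if imaging change says nothing about symptom change inside either cluster. The sponsor expects both shifts: the Objectives hypothesise increased perfusion and reactivity, and the Background reports clinical gains over placebo in the earlier randomized trial.

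This is the only planned analysis of the link between imaging and clinical change. A correlation produced by arm means would show that the device affects both, which the group comparisons already show, and could be misread as evidence that one explains the other.

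**Working it through.** **Inputs.** From the documents: up to 20 participants, 1:1 allocation, hence 10 per arm. Assumed, because the documents give none: standardized device effects d1 (imaging change) and d2 (clinical change), a two-sided 0.05 test, normal data with unit within-arm SD, Pearson correlation, no association within either arm, and an identical device response in every participant. The plan states no figure for the correlations, so there is nothing to reproduce.

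**Correlation created by arm means alone.** With equal arms,

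r = (d1·d2/4) / √[(1 + d1²/4)(1 + d2²/4)].

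At d1 = d2 = 1.0: 0.25/1.25 = 0.20. At 1.5: 0.5625/1.5625 = 0.36. At 1.0 and 0.5: 0.125/√(1.25 × 1.0625) = 0.11. If either effect is zero, r = 0, so both outcomes must move.

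**False-positive rate** (200,000 simulated trials per setting, 10 per arm; pooled test on 18 df, arm-adjusted on 17 df):

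| d1 / d2 | r from arm means | Pooled | Arm-adjusted |
|---|---|---|---|
| 0.5 / 0.5 | 0.06 | 5.7% | 5% |
| 0.8 / 0.8 | 0.14 | 9.0% | 5% |
| 1.0 / 1.0 | 0.20 | 13.8% | 5% |
| 1.5 / 1.5 | 0.36 | 37.7% | 5% |
| 0.8 / 0.5 | 0.09 | 6.5% | 5% |
| 1.0 / 0.5 | 0.11 | 7.4% | 5% |
| 1.5 / 0.5 | 0.15 | 9.5% | 5% |

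With 8 per arm and equal effects of 0.5, 0.8, 1.0 and 1.5, the pooled rates are 5.6%, 8.1%, 11.7% and 30.4%.

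**Active arm only.** There is no arm-mean artefact, but with n = 10 significance needs |r| > 0.63, and power is 33% if the true within-arm r is 0.5.

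**What adjustment does not remove.** Suppose there is no mediation, but individual response to the device varies and drives both outcomes. They then correlate inside the active arm. With response SD at half its mean, the arm-adjusted test rejects in 7.5% of trials at d = 1.0 and 15.1% at d = 1.5 (pooled: 22.2% and 57.4%). With response SD at 75% of its mean, the arm-adjusted rates are 15.3% and 38.4%, still below pooled. The 5% column therefore holds only for a uniform response.

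**Power if mediation is true** (within-arm r = 0.5, 10 per arm):

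| Imaging effect (SD) | Pooled | Arm-adjusted |
|---|---|---|
| 0 | 64.2% | 61.6% |
| 0.5 | 66.7% | 61.7% |
| 1.0 | 73.6% | 61.7% |
| 1.5 | 82.1% | 61.5% |

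The 2.6-point gap at zero effect is the price of the smaller information in the adjusted test. The growth beyond that is the between-arm difference, the same component that produces the false positives.

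**Precision** (Fisher z, observed r = 0.5, z = 0.549). One arm of 10: 0.549 ± 1.96/√7 gives −0.19 to 0.86. Arm-adjusted, n = 20 with one covariate: 0.549 ± 1.96/√16 gives 0.06 to 0.78.

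**The case against.** The strongest reply is that the harm is doubly conditional: the arms must be pooled, and the device must have a large effect on both outcomes. The text can be read as active arm only, and no effect size or SD is given. At modest or unequal effects the inflation is a few points, and the largest figure needs 1.5 SD on both outcomes. This stands, and it limits the size of the point.

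A second reply is that nothing hangs on the analysis: it is exploratory, with no decision rule and no stated alpha. This also stands. It makes the change a cheap improvement.

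A third is that reporting by group already protects the reader. Only in part: it shows that both outcomes shifted by arm, but not whether they go together within arms.

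A fourth is that adjustment discards the randomized part of the relation and loses power if mediation is true. The loss is real, which is a reason to keep the pooled correlation on display. But that between-arm part cannot distinguish mediation from two parallel device effects.

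A reader might infer that the plan commits to pooling. It does not; it is silent. A reader might also infer that a within-arm association would settle the mechanism. It would not, because a shared, varying response produces one without mediation.

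**Conclusion.** The gap is real and worth closing. Run as written on all participants, the correlation can support an unsound mechanism conclusion. Under the stated assumptions the pooled false-positive rate is about 6% to 14% for equal effects of 0.5 to 1.0 SD, 38% at 1.5 SD, and 6.5% to 9.5% for the unequal pairs tried. Effects above about 1 SD on both outcomes, where the problem becomes material, are neither supported nor ruled out by the documents.

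It would be wrong to conclude that the trial's main findings are at risk. The randomized ANCOVA comparisons of perfusion and reactivity are mechanism evidence in their own right and are unaffected.

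**What to change.** Add to the Analysis Plan:

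> For each change-score time point (end of treatment and follow-up), the imaging–clinical association will be estimated adjusted for arm (partial correlation given arm, or regression of clinical change on imaging change plus arm). By-arm estimates with 95% CIs will be shown, with the pooled correlation beside them as description. A positive result will be described as consistent with a mechanism, not as proof of one.

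The by-arm estimates are needed because the adjusted estimate assumes one common slope; they will be imprecise. The last sentence is needed because adjustment leaves within-arm confounding in place. Blinding needs no new step, since blinded analysts running a group-wise ANCOVA already need coded arms.

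The cost is a few sentences, no new data, one degree of freedom (critical |r| rises from 0.44 to 0.46), and the loss of power shown in the working if mediation is true.
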